2.5.2.2 Small animal ^{68}Ga -HBED-CC and repeatability

Several experiments were performed in mice to determine repeatability of the ^{68}Ga -HBED-CC which are published at Molecular Imaging and Biology with the following figures representing a synopsis of the results.

Representative PET images of mice bearing PC3-PIP xenografts imaged with ^{68}Ga -HBED-PSMA on three consecutive days

Normalized uptake values in mice bearing PC3-PIP tumor xenografts that were imaged using ^{68}Ga -HBED-PSMA either consecutively for three days (Group 2, mice 4, 5, and 6) or alternative days with ^{68}Ga -HBED-PSMA and administered with ^{68}Ga -HBED-PSMA on day 2 (Group 1, mice 1, 2, and 3) one hour post-administration of tracer.

3. Study Design

3.1 Overall Design

Thirty patients with metastatic prostate cancer that have undergone standard-of-care staging at WCMC will be considered for enrollment. For this study, enrolled patients will undergo a total of two whole-body dynamic ^{68}Ga -PET scan protocols of at least 0-75 min and at most 0-90 min scan time post injection, depending on the amount of injected dosage. A 6 to 48 hour gap will be introduced between the two scans. The first scan will occur after a baseline clinical evaluation, which will include a history, physical, and baseline lab draw. Blood work will be obtained before, during and after the scan. The radiotracers will be evaluated for repeatability and equivalence across the different production methods. This will include basic pharmacokinetics, distribution, metabolism and excretion.

Up to 30 patients will undergo each two whole-body dynamic scans, initially with ^{68}Ga -PSMAcyc and later with ^{68}Ga -PSMagen (with a minimum time of 6 h and maximum time of 2 days between the two injections). All patients will receive ^{68}Ga -PSMagen from the CBIC core and ^{68}Ga -PSMAcyc from NCM pharmaceuticals at a specific activity of 1-2 Ci/ μmol , the typical specific activity used in published clinical trials with ^{68}Ga -PSMA (10).

3.2 Scientific Rationale for Study Design

This is a single-arm study.

3.3 Justification for Dose

Patients will be injected with 100-300 MBq of ^{68}Ga -HBED-PSMA (from either the generator or cyclotron source) via a catheter. ^{68}Ga -PSMA PET/CT will be acquired using a Siemens Biograph mCT™ PET/CT scanner. Please see details in section 7.1.

The goal is to administer this amount of the imaging probe labeled with 2.5 MBq of ^{68}Ga per kg body weight with a minimum of 100 MBq and maximum of 300 MBq ^{68}Ga per patient.

The whole-body dynamic ^{68}Ga -PSMA scans will involve an initial dynamic scan at a pelvic scanner bed position centered over the prostate tissues for the first 10min post injection (p.i.), followed by multiple successive whole-body scans (passes) at least 10-75 min and at most 10-90 min post injection, depending on the amount of injected dosage. A fixed scan time of 30sec per bed position per pass will be used with an adjustable total number of passes. The PET data collected from at least the last six passes will be summed at each bed position and combined over all bed positions to produce whole-body static ^{68}Ga -PSMA images equivalent of a total acquisition time of $6 \times 30 \text{ sec} = 180\text{sec}$ or 3 min/bed position from all summed passes.

Due to the short physical half-life of ^{68}Ga and the decreasing elution efficiency of the $^{68}\text{Ge}/^{68}\text{Ga}$ generator during its lifetime, the amount of radioactivity injected per patient will necessarily vary. If the amount of activity per kg body weight differs by more than 25% from the recommended dose of 2.5MBq/kg of body weight, the effective total acquisition time per bed position from all passes will be adjusted by increasing the total number of passes, in increments of one pass, while keeping fixed the scan time per bed per pass. The adjustment of the total number of passes will result in the respective adjustment of the total scan time up to 90 min post injection. The total number of passes will be adjusted such that the product of total acquisition time per bed position from all summed passes participating in the synthesis of the equivalent static PET images and of the injected activity is at least 7.5 MBq/kg*min or the total scan time reached 90 min.

In the meantime, the dynamic PET data from all passes will also be analyzed at each bed position on voxel-by-voxel analysis according to the Patlak graphical model to estimate ^{68}Ga -PSMA net uptake rate (Ki) whole-body images. The acquired PET data will be corrected for attenuation and scatter and adjusted for system sensitivity. Multiple parametric PET images in terms of standardized uptake values (SUV) (= MBq measured/gm tissue / MBq injected/gm body mass) and net tissue uptake rate Ki (= (MBq measured in tissue/gm tissue / MBq measured in blood plasma/ ml plasma) / post injection time) will be provided.

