7.1 Study Intervention/Patient scans

Protocol initiation quality assurance

Patient scans will be acquired on one of the Siemens Biograph mCT™ PET/CT scanners with a preference for the same instrument on all scans. Quality assurance images from each system will be acquired at the beginning of the protocol on all mCT scanners using a ^{68}Ga -filled 20-cm-diameter cylindrical water phantom with average SUVs in the range $1.0 \pm 0.5 \text{ g/ml}$ with no artifacts on visual inspection.

Individual patients preferably use the same scanner system for both scans.

Prior to imaging evaluation, patients will be permitted to eat a light meal.

An intravenous catheter (Hep-Lock) will be placed in the CBIC or WCINYP for radiopharmaceutical administration, scans, and blood sampling.

Patient scans

Two dynamic whole body ^{68}Ga -PSMA PET/CT scans will be performed successively at least 6 hours apart. As there will be an accumulation of activity in the urinary bladder, patients will have pre-treatment hydration and encourage voiding immediately prior to imaging, however the short half-life of ^{68}Ga should not result in imaging counts from the first scan to appear on the latter scan.

PET/CT imaging patients will be positioned on a flat couch in radiation treatment position. Custom-made immobilization devices, skin markings, PET/CT gantry, and room lasers will be used to ensure accurate and reproducible positioning. Imaging will start with low-dose CT scan (80 mA) for attenuation correction, followed by a PET scan. A low dose CT scan (80 mA) will be performed over the prostate or a pre-determined index lesion. A 10min dynamic PET scan at the pelvic bed position, centered over the prostate tissues, will be initiated concurrently with an intravenous bolus injection of approximately 2.5MBq/kg of body weight ($\pm 10\%$) of ^{68}Ga -PSMA, followed by a time series of whole-body PET scans (passes) at least 10-75 min and at most 10-90 min post injection. The PET acquisition time per bed position per pass will be fixed at 30sec and the total number of passes summed post acquisition to produce the static ^{68}Ga -PSMA PET images will be at least six. The total number of late passes may be increased, if needed, such that the product of total acquisition time per bed position from all passes and injected activity is at least 7.5 MBq/kg*min or a total acquisition time of 90min is reached.

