Moreover, the number of bed positions will be adjusted to cover a field of view from top of the skull to mid-thigh of an average human adult for each pass. All PET scans will be conducted with patients in a supine position with the arms comfortably positioned and secured by the side of the patient. All whole-body PET passes of each subject will be uni-directional, i.e. they will be performed along the same axial direction (cranio-caudal or caudo-cranial).

The PET data from at least the last six whole-body scan passes will be summed up and reconstructed at each bed position such that the product of total acquisition time per bed position from all passes and injected activity is at least 7.5 MBq/kg*min or a total scan time of 90min is reached. The resulting composite static PET images will then be combined with the same method as that employed for conventional static PET images at each bed position and the composite Standardized Uptake Value (SUV) static PET images will be calculated. In the meantime, the dynamic ⁶⁸Ga-PSMA concentration in the blood plasma (input function) will also be derived from the dynamic PET images at the pelvis, as estimated from the 0-10min p.i. of the initial dynamic pelvic PET scan and the corresponding pelvic beds of the subsequent set of whole-body PET passes. For that purpose, regions of interest will be drawn in the lumen of the abdominal section of the descending aorta that is included in the pelvic bed position. The blood pool image regions will be drawn as far as possible from the neighboring aortic wall to minimize any partial volume effects. The image derived input function data will then be fitted to the measured blood samples data for validation and enhanced accuracy. Subsequently, the images from all the dynamic PET whole-body passes and the image-derived input function will be fitted to the Patlak graphical model on a voxel-by-voxel basis to produce whole-body ⁶⁸Ga-PSMA net uptake rate constant (Ki) images. During the PET scan procedure, the patient will be allowed to get off from the couch in between the dynamic whole-body passes, if required (such as for a bathroom break).

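### The SUV time window depends on injected activity and is not matched between a patient's two scans, which adds within-subject variation to the primary comparison

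*Combined protocol and SAP*

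**What the plan says.** - **Acquisition (Section 3.3).** Whole-body passes run "at least 10-75 min and at most 10-90 min post injection, depending on the amount of injected dosage". Each bed gets 30 s in every pass, and only the count of passes changes.
- **Static image.** Section 3.3: "The PET data collected from at least the last six passes will be summed at each bed position". Section 7.1 repeats this: "The PET data from at least the last six whole-body scan passes will be summed up and reconstructed at each bed position".
- **Count rule.** Passes are added until the product of injected activity and summed time per bed position "is at least 7.5 MBq/kg*min or the total scan time reached 90 min". Section 3.3 invokes the adjustment when activity is more than 25% away from 2.5 MBq/kg. Section 7.1 gives no trigger and says "The total number of late passes may be increased, if needed". Section 3.3 adds that the adjustment "will result in the respective adjustment of the total scan time up to 90 min post injection".
- **Expected variation.** Section 3.3 accepts that "the amount of radioactivity injected per patient will necessarily vary", and gives two reasons: the short half-life of the nuclide and the falling yield of an ageing generator.
- **Second scan and analysis.** Section 7.1 says only that the same procedures apply to the second scan. Section 12 compares SUVmean and SUVmax of copied regions through the within-subject coefficient of variation (CV), with a 30% limit and no term for uptake time.
- **Activity limits.** The dosimetry table in Section 2.4.1 gives a maximum of 3.3 mCi per session. Section 3.3 allows 100-300 MBq. Section 7.1 specifies about 2.5 MBq/kg within 10%.

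**The concern.** SUV is a ratio at a point in time. If tissue uptake is still changing at 60-90 min, two images centred on different times give different SUVs even when the two products behave identically. The plan's own Patlak analysis models tissue uptake as a function of time after injection, so time dependence is not foreign to it.

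Here the window follows injected activity, activity is expected to vary, and nothing ties the second scan's window to the first. The resulting difference falls directly into the paired SUV contrast. At the least it inflates the within-subject CV and makes the 30% criterion harder to meet for a reason unrelated to production method. If activity also differed systematically by product, the mean difference would be shifted as well. The products are given without randomization (Section 7.11), so the allocation would not balance such a difference, and a larger sample would not remove it.

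**Working it through.** **1. The plan's own figure.** Six passes × 0.5 min × 2.5 MBq/kg = 7.5 MBq/kg·min. This reproduces the count target in Section 3.3.

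**2. Passes needed.** At activity *a* (MBq/kg), n = max(6, ⌈7.5 / (0.5*a*)⌉):

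| *a* (MBq/kg) | 2.5 or more | 2.25 | 1.875 | 1.5 | 1.25 |
|---|---|---|---|---|---|
| n | 6 | 7 | 8 | 10 | 12 |

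An 80 kg patient given 200 MBq on one day and 100 MBq on the other, both inside the Section 3.3 range, has *a* = 2.5 and 1.25, so 6 passes against 12.

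**3. Window midpoint.** The bed count is not in the documents; 6-10 beds are assumed. Pass length is d = beds × 0.5 min. The midpoint of six passes ending at 75 min is 75 − 3d. The number of whole passes that fit between 75 and 90 min is m = ⌊15/d⌋. Summing the original six plus m added passes moves the midpoint by m·d/2. Summing only the last six moves it by m·d.

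| Beds | d (min) | Midpoint, end at 75 | m | Shift, added passes summed (min) | Shift, last six only (min) |
|---|---|---|---|---|---|
| 6 | 3.0 | 66.0 | 5 | 7.5 | 15 |
| 7 | 3.5 | 64.5 | 4 | 7.0 | 14 |
| 8 | 4.0 | 63.0 | 3 | 6.0 | 12 |
| 10 | 5.0 | 60.0 | 3 | 7.5 | 15 |

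The last column does not fit the count rule: six passes give 3 min per bed, and 3*a* is below 7.5 whenever *a* is below 2.5. The maximum consistent with the rule's purpose is therefore about 6-7.5 min.

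**4. Direction.** A minimum of six late passes does not settle which extra passes are summed. If the 12 passes needed at 1.25 MBq/kg were all taken before 75 min, the midpoint would be 75 − 6d. That is 3d, or 9-15 min, earlier than the six-pass midpoint.

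**5. Under the Section 7.1 tolerance.** The lowest activity is 0.9 × 2.5 = 2.25 MBq/kg, which needs seven passes. The shift is d/2 = 1.5-2.5 min with all seven summed. The 25% trigger (0.75 × 2.5 = 1.875 MBq/kg) is never reached.

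**6. Effect on SUV.** The documents give no slope. Assuming a change of 0-1% per min, of either sign by region:
- 7.5 min × 0-1% = 0-7.5%;
- 2.5 min × 0-1% = 0-2.5% under the 10% tolerance.

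The SD of two values is their difference divided by √2. A pair differing by 7.5% from this cause alone thus has a within-pair CV of 7.5/√2 ≈ 5.3%.

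**7. Activity limits.** 3.3 mCi × 37 = 122 MBq. At 2.5 MBq/kg that maximum is exceeded by any patient above 122/2.5 ≈ 49 kg, so Section 2.4.1 cannot stand beside the Section 3.3 target. If it did apply, an 80 kg patient given 100-122 MBq would need 10-12 passes on both days, and the two windows would nearly coincide.

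**The case against.** A reader might infer that the generator scan will tend to be the later-window scan, because Section 3.3 mentions declining generator yield, and that the comparison is therefore biased by product. The documents do not support this. Both products share the 2.5 MBq/kg target, and no activity by product is given. Section 3.3 also names the short half-life, which affects the cyclotron product too: it depends on nuclide made by an outside company (Section 2.5.2) and is shipped in the afternoon (Section 7.11). Which product would arrive with less activity is undetermined.

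Three further objections have weight.
- **The 10% tolerance nearly removes the problem.** This stands if that tolerance governs. But Section 3.3 allows a far wider range and says activity will vary, and Section 7.1 itself keeps the extension to 90 min. The conflict leaves the size open; it does not show that it is negligible.
- **The slope could be zero or negative.** This stands. Section 12 includes reference regions as well as lesions, and both the existence and the sign of the effect depend on the region.
- **The pass rule protects image counts, and SUVmax is sensitive to noise.** This is a fair reason for the rule. It argues against a common window only if that window is short of counts. Every scan covers at least 10-75 min. Those 65 min hold 13-21 whole passes of 5-3 min, enough for the 12 needed at 1.25 MBq/kg.

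**Conclusion.** The concern holds as a matter of unmatched uptake windows. As written, the plan can read a patient's two scans at different post-injection times, with no matching and no adjustment. This adds within-subject variation to the primary measure. Bias between products is possible but conditional on a systematic difference in injected MBq/kg that the documents do not show.

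The size is modest: a midpoint shift of up to about 6-7.5 min and an SUV difference of about 0-7.5%, against the 30% criterion. This rests on two assumptions from outside the documents: 6-10 bed positions, and an SUV change of 0-1% per min. Larger figures, from a shift of 12-15 min, need a reading of the summation rule that misses the plan's own count target at low activity. How often windows differ at all depends on which of the conflicting activity limits applies.

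**What to change.** A cheap improvement, made by reprocessing passes already acquired:

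- For the primary SUV analysis, build both static images of a patient from the same post-injection interval, using passes available in both scans.
- If the lower-activity scan needs more passes to reach 7.5 MBq/kg·min, add the same earlier passes to both images.
- Report injected activity and window midpoint by product, so that any systematic difference is visible.
- Keep the image built by the current rule as a sensitivity analysis.
- Reconcile the activity limits in Section 2.4.1 (3.3 mCi maximum), Section 3.3 (100-300 MBq, 25% trigger) and Section 7.1 (within 10%). State in the same place which passes are summed.

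The cost is a somewhat earlier or longer common window and fewer counts in some images. At very low activity with long passes the target may be missed: 1.0 MBq/kg needs 15 passes, while 65 min holds 13 passes of 5 min. Matching the passes also leaves counts differing in proportion to activity. At 12 passes (6 min per bed), 2.5 and 1.25 MBq/kg give 15 and 7.5 MBq/kg·min, so both meet the target but are not equal in noise. No extra injection, scan or visit is needed.

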1.2.3 Exploratory Objectives

- Investigate repeatability of whole-body ^{68}Ga -PSMA-generator Ki Patlak imaging against that of conventional whole-body ^{68}Ga -PSMA-generator SUV imaging in patients with confirmed metastatic PCa.
- Evaluate equivalence of whole-body ^{68}Ga -PSMA Ki Patlak imaging between the two processes to create ^{68}Ga -HBED-PSMA (68GA -PSMA-cyclotron vs. 68Ga -PSMA-generator).

2. Background

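### Section 3.3 defines the exploratory measure Ki in two ways that are not equivalent: as a Patlak fit, and as one tissue-to-plasma ratio divided by clock time

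*Combined protocol and SAP*

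**What the plan says.** Section 3.3 first describes a "voxel-by-voxel analysis according to the Patlak graphical model to estimate" the net uptake rate Ki. In the same paragraph it lists the parametric images to be produced and defines the second of them as "net tissue uptake rate Ki (= (MBq measured in tissue/gm tissue / MBq measured in blood plasma/ ml plasma) / post injection time". This is the only explicit formula for Ki in the documents.

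Section 7.1 sets out the Patlak route in more detail. The plasma input function "will also be derived from the dynamic PET images at the pelvis", using the 0-10 min pelvic scan and the later pelvic beds, and is checked against blood samples. Then "the images from all the dynamic PET whole-body passes and the image-derived input function will be fitted to the Patlak graphical model" voxel by voxel. Neither section gives a start time for the linear part of the Patlak plot.

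Scan length is not fixed. Section 3.3 has the whole-body passes run "at least 10-75 min and at most 10-90 min post injection, depending on the amount of injected dosage". It lengthens the acquisition under a rule that begins "If the amount of activity per kg body weight differs by more than 25% from the recommended dose".

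Ki appears only in the exploratory objectives (section 1.2.3): its repeatability against that of SUV, and its equivalence between the two production methods. The primary endpoint and the 30% agreement criterion in section 12 use SUVmean and SUVmax.

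**The concern.** The Patlak Ki is a slope: tissue/plasma is regressed on the plasma integral divided by the current plasma concentration, with a separate intercept. Its purpose is to separate the net uptake rate from the shape of the plasma curve. The parenthetical formula does not do this. It takes one tissue/plasma ratio at one time and divides by minutes since injection.

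An analyst who followed the formula would obtain a different quantity from one who followed section 7.1. Under the formula, a difference between a patient's two sessions in plasma clearance or scan end time would show up as a Ki difference even if the net uptake rate were identical. That would blur both exploratory comparisons. If both definitions stay in the protocol, the choice between them could also be made after the data are seen.

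A second, smaller gap lies in the Patlak route itself. All passes from 10 min enter the fit, no linear-phase start is set, and nothing requires the same window for both scans of a pair.

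**Working it through.** The documents state no numerical Ki result, so there is no figure to reproduce. The check is algebra, followed by an illustration on assumed kinetics.

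**Algebra.** Let C_T be tissue concentration, C_p plasma concentration, V the intercept and t the time since injection. The Patlak model is

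C_T(t)/C_p(t) = Ki × θ(t) + V, with θ(t) = ∫₀ᵗ C_p / C_p(t).

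Dividing by t gives the quantity in the section 3.3 parenthesis:

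[C_T(t)/C_p(t)]/t = Ki × θ(t)/t + V/t.

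This equals Ki only if θ(t) = t (constant plasma) and V = 0. Section 7.1 specifies an intravenous bolus, so by the time of the late passes plasma has fallen, θ(t) exceeds t, and the formula overstates Ki.

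**Assumed inputs (none are in the documents).** C_p(t) = a·exp(−ln2·t/h1) + (1−a)·exp(−ln2·t/h2), with fast fraction a = 0.6 to 0.8, fast half-life h1 = 2 to 4 min, slow half-life h2 = 40 to 90 min, and V = 0. The ratio of the formula to true Ki is then θ(t)/t. The two ends of the range are:

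| a, h1, h2 | t (min) | ∫C_p | C_p(t) | θ (min) | θ/t |
|---|---|---|---|---|---|
| 0.6, 2, 90 | 75 | 24.52 | 0.2245 | 109.2 | 1.46 |
| 0.6, 2, 90 | 90 | 27.70 | 0.2000 | 138.5 | 1.54 |
| 0.8, 4, 40 | 75 | 13.01 | 0.0545 | 238.6 | 3.18 |
| 0.8, 4, 40 | 90 | 13.73 | 0.0420 | 326.6 | 3.63 |

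- **Level:** 1.46 to 3.18 times true Ki at 75 min, and 1.54 to 3.63 times at 90 min.
- **Scan end time:** the 90 min value over the 75 min value, minus 1, runs from +2.8% (a = 0.8, h1 = 4, h2 = 90) to +16.5% (a = 0.6, h1 = 2, h2 = 40).
- **Clearance:** shortening only h2 by 10% raises the 75 min value by 3.8% (a = 0.6, h1 = 2, h2 = 90) to 11.5% (a = 0.8, h1 = 4, h2 = 40).

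**Non-zero intercept and wider kinetics.** With V = 0.05 to 0.3 ml/g, Ki = 0.02 to 0.1 ml/g/min, a = 0.8, h1 = 3 min and h2 = 30 to 120 min, the formula gives 1.6 to 4.2 times true Ki at 75 min. The change from 75 to 90 min runs from −0.3% to +23%, so a rise with later readout is usual but not universal. Even with constant plasma, V/(Ki × 75) adds 0.7% (0.05/(0.1 × 75)) to 20% (0.3/(0.02 × 75)).

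**Patlak slope on the same simulated data.** Fitted from 30 min, it returns 1.00 times true Ki in every one of these scenarios, whether the fit ends at 75 or 90 min.

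**Fit window.** In noise-free checks with assumed irreversible two-tissue kinetics, fitting from 10 min gave a Ki between about 5% low and 15% high, depending on the rate constants assumed. Fitting from 30 min gave about 3% low to 7% high. These figures are indicative only.

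**The case against.** The strongest reply is that Patlak is plainly the operative method. Section 3.3 names it before giving the formula, section 7.1 sets out the steps, and the exploratory objectives call the measure Ki Patlak imaging. A single-time ratio would need neither the early pelvic input function nor a multi-pass fit. The parenthesis sits beside a similar unit-by-unit gloss for SUV, and its units (ml/g/min) are right for Ki. This largely stands: the formula may be no more than loose wording. It does not remove the conflict, because the formula is the only explicit one given and it is not what a Patlak fit produces.

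On size, a constant overstatement would cancel in a within-patient ratio, so the 1.5- to 3.2-fold figure alone would not create a difference between products. That also stands. What matters for the paired comparison is a change between sessions in clearance or readout time.

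A reader might infer more than the documents support, in four ways:

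- **That the Ki endpoint is in fact distorted.** This would follow only if the parenthetical formula were computed in place of the fit in section 7.1.
- **That scan time could move Ki by about a third.** That comes from comparing 60 with 90 min under the same assumed kinetics. The protocol's end times are 75 and 90 min.
- **That clearance could move Ki by 40% to 50%.** That requires the slow half-life to go from 90 to 40 min between two sessions of one patient at most 48 h apart. Nothing in the documents supports so large a shift.
- **That the equivalence conclusion or sample size is affected.** The primary endpoint is SUV, and no margin, decision rule or sample size rests on Ki.

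Fitting from 10 min already omits the earliest phase, so the missing start time is incomplete detail rather than a serious flaw. It remains worth closing, because it applies even if the parenthesis is read as a gloss.

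**Conclusion.** The point holds as an inconsistency in the definition of an exploratory measure. Section 3.3 contains two definitions of Ki that agree only under constant plasma and zero intercept, and the bolus injection rules out the first of these. That conclusion, and the dependence on the plasma curve, follow from algebra alone.

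The size rests on assumed kinetics. With bi-exponential plasma and zero intercept, the formula gives about 1.5 to 3.2 times true Ki at 75 min. A 90 rather than 75 min readout adds about 3% to 16%, and a 10% shorter slow plasma half-life adds about 4% to 11%. These errors occur only if the written formula is used. The unspecified fit window is a lesser gap in the Patlak route itself. The correction should be made, but nothing here bears on the primary SUV comparison.

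**What to change.** 1. In section 3.3, replace the parenthetical definition with: Ki = the slope of C_tissue(t)/C_plasma(t) regressed on ∫₀ᵗ C_plasma / C_plasma(t), with a free intercept.
2. In sections 3.3 and 7.1, replace the fit to all passes with a fit to passes after a prespecified start time t*.
3. Use the same start and end times for both scans of a patient. Where one scan ran longer, end both fits at the earlier end time.
4. Choose t* from the linearity of the Patlak plots, and fix it before the reader or analyst learns which scan used which product. This fits the blinding already described in section 7.11.

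The cost is protocol and analysis wording. The planned acquisition already supplies the input function and the passes, so no scan, visit or dose changes. The downside is that fewer passes enter the fit, which makes voxel-level Ki slightly noisier.
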